## **21. Publication Policy and Secondary Use of Data**

### **21.1 Publication Policy**

The Sponsor maintains the right to use the results of this study in their original form and/or in a global report for submission to governmental and Regulatory Authorities of any country.

The results of the study may be presented during scientific symposia or published in a scientific journal only after review by the Sponsor in accordance with the guidelines set forth in the applicable publication or financial agreement.

The timing, presenter and other matters are determined through discussion between the Coordinating Investigator and the Sponsor.

### **21.2 Secondary Use of Data**

The Sponsor maintains the right to secondary use of data in this study. Secondary use of data describes the use of data from this study for other study/studies (including an external offering).

Specifically, secondary use of data may include:

- Use for analysis of other study.
- Use for integrated analysis with data from one or more associated study/studies.
- Utilization to regulatory authorities for their own analysis and the sharing of information with other regulatory authorities.
- Use for epidemiology study.

## **22. Ethics**

### **22.1 Ethical Considerations**

It is mandatory that all considerations regarding the protection of patients be carried out in accordance with the latest versions of the protocol, GCP, ICH Guidelines, the ethical principles that have their origin in the Declaration of Helsinki, and all applicable regulatory requirements.

### **22.2 Institutional Review Board**

The study must be approved by an appropriately constituted IRB, as required in GCP or ICH E6 Guidelines. Prior to conduct, the study must be reviewed and approved by the IRB of the study site, and approved by the director of study site.

The Investigator is responsible for obtaining renewal of approval during the clinical study. Timeframes for renewal will be based on IRB requirements but renewal at least annually is required by regulations. At the end of the study, the Investigator will notify the IRB of the study site of the conclusion of the study and its outcome.

### **22.3 Informed Consent Procedure**

Informed consent must be obtained in compliance with the guidelines provided in the GCP, Declaration of Helsinki, ICH E6 Guideline and local regulations.

The Investigator and Sub-investigator must fully inform patients of all pertinent aspects of the study. All participants should be informed to the fullest extent possible about the study in a language and in terms they are able to understand.

Prior to participation in the study, the written ICF is to be signed and personally dated by the patient and the person who provided the explanation for ICF. A copy of the signed and dated ICF must be given to the patient. The ICF used must have had prior approval by the IRB.

By signing and dating the ICF prior to the implementation of the study procedures set forth in this protocol, the patient is deemed to have consented to participate in the study.

Prior to the study enrollment, a copy of the ICF signed and dated by the patient must be given to him/her prior to any study-related procedures described in the ICF are undertaken.

The Investigator must prepare the ICF using a proposed ICF provided by the Sponsor as reference. When the ICF needs to be revised, the Investigator must discuss with the Sponsor, prepare a revised version and use the version approved by the IRB.

### **23. Study Administrative Structure**

For details, see the attached document.

## 25. Appendices

STATISTICAL ANALYSIS PLAN

Version 3.0

Name of Investigational Product	TAS-303
Title of Study	A phase IIa study of TAS-303 in female patients with stress urinary incontinence
Protocol number	10060050
Date of preparation or revision	September 4, 2018
Author	

History of preparation and revision

Date	Author	Reason for preparation or revision
March 20, 2018		Preparation of the first version
May 29, 2018		Prior to the key code breaking, details of analyses were changed according to results of blinded review.
September 4, 2018		Contents were added because it was an additional analysis.

Date and Signature

Person in charge of statistical analysis	MM DD, YYYY	
Responsible person for statistical analysis	MM DD, YYYY	
Taiho Pharmaceutical Co., Ltd. Statistical Team Leader	MM DD, YYYY	

Changes in Statistical Analysis Plan

Version 1.0 (March 20, 2018) to Version 2.0 (May 29, 2018)

Item	Before change	After change	Reason for change
5	Blinded Review	Blinded Review	Japanese notation was changed.
6.2.1 Table 6-2	_	Age Category 2 < 60 years, ≥ 60 years	Category was added according to results of blinded review.
7.3 8.1.1 8.1.7 8.1.8	Baseline values and allocation adjustment factors (status of urinary incontinence, mean incontinence episode frequency (IEF) per 24 hours [≥ 2 per day, < 2 per day]) were used as covariates.	Allocation adjustment factors (status of urinary incontinence, mean IEF per 24 hours [\geq 2 per day, $<$ 2 per day]), and age ($<$ 60 years and \geq 60 years) were used as covariates.	Covariates were changed according to results of blinded review.
7.3	Intergroup comparison will be conducted using the placebo group as the control by the van Elteren test ⁵⁾ using allocation adjustment factors as strata.	Intergroup comparison will be conducted using the placebo group as the control by the van Elteren test ⁵⁾ using allocation adjustment factors and age (< 60 years and ≥ 60 years) as strata. If any stratum includes a group with 0 patient, the test will be conducted by excluding age from the strata. The van Elteren test will be performed in two patterns, i.e., a pattern in which allocation adjustment factors at the time of enrollment are used as strata (analysis in the FAS only) and a pattern in which allocation adjustment factors recorded in CRF are used as strata.	Stratification factors were added according to results of blinded review. Moreover, details of stratification factors were added.
8.1.1	The van Elteren test using allocation adjustment factors as strata will be conducted.	The van Elteren test using allocation adjustment factors and age (< 60 years and ≥ 60 years) as strata will be conducted. If any stratum includes a group with 0 patient, the test will be conducted by excluding age from the strata. The van Elteren test will be performed in two patterns, i.e., a pattern in which allocation adjustment factors at the time of enrollment are used as strata (analysis in the FAS only) and a pattern in which allocation adjustment factors recorded in CRF are used as strata.	Stratification factors were added according to results of blinded review. Moreover, details of stratification factors were added.

Item	Before change	After change	Reason for change
8.1.7	The van Elteren test using allocation adjustment factors as strata will be conducted. The van Elteren test will be performed in two patterns, i.e., a pattern in which allocation adjustment factors at the time of enrollment are used as strata and a pattern in which allocation adjustment factors recorded in CRF are used as strata.	The van Elteren test using allocation adjustment factors and age (< 60 years and ≥ 60 years) as strata will be conducted. If any stratum includes a group with 0 patient, the test will be conducted by excluding age from the strata. The van Elteren test will be performed in two patterns, i.e., a pattern in which allocation adjustment factors at the time of enrollment are used as strata (analysis in the FAS only) and a pattern in which allocation adjustment factors recorded in CRF are used as strata.	Stratification factors were added according to results of blinded review. Moreover, details of stratification factors were added.
8.1.8		For percent changes (Weeks 4 and 8 of treatment) and changes (Weeks 4 and 8 of treatment) from baseline to each time point of evaluation, student's t-test, Wilcoxon's rank sum test, and van Elteren test using allocation adjustment factors and age (< 60 years and ≥ 60 years) as strata will be conducted using the placebo group as the control. If any stratum includes a group with 0 patient, the test will be conducted by excluding age from the strata. The van Elteren test will be performed in two patterns, i.e., a pattern in which allocation adjustment factors at the time of enrollment are used as strata (analysis in the FAS only) and a pattern in which allocation adjustment factors recorded in CRF are used as strata.	Stratification factors were added according to results of blinded review. Since tests for the mean frequency of UUI episode per 24 hours were not mentioned, they were added.

Version 2.0 (May 29, 2018) to Version 3.0 (September 4, 2018)

Item	Before change	After change	Reason for change
8.1.1 8.1.2 8.1.5 8.1.7 8.1.8	Fisher's exact test will be conducted.	Fisher's exact test with placebo as control will be conducted.	Since Fisher's exact test uses the placebo as the control, the statement was added.
8.1.5	-	The proportion of improvement (Very much better and Much better) at the time of enrollment and Weeks 4 and 8 of treatment and 95% CI will be calculated, and Fisher's exact test with placebo as the control will be conducted.	The statement was added because it was an additional analysis.
8.1.10 8.1.11 8.1.12 8.1.13 8.1.14 8.1.15 8.1.16 8.1.17		(Addition of items)	Analytical items were added because it was an additional analysis.
8.3.1		The number of patients and the incidence will be displayed by severity (incidence ≥ 2%) for each item of adverse event. ADRs will be analyzed in the same way.	The statement was added because it was missing.
8.3.3	-	The incidence of abnormal variations in 12-lead ECG will be calculated.	The statement was added because it was missing.
8.3.3	-	For amounts of changes in measured values of the QTcF interval and heart rate from values immediately before start of treatment to each evaluation time point, student's t-test will be conducted using the placebo group as the control.	The statement was added because it was an additional analysis.

1. SCOPE AND PURPOSE

This plan specifies details of the statistical analysis plan for "a phase IIa study of TAS-303 in female patients with stress urinary incontinence" (Protocol No. 10060050).

2. STUDY DESIGN AND TARGET SAMPLE SIZE

2.1. Study Design

This clinical trial is a multicenter, randomized, double-blind, placebo-controlled parallel-group study with central enrollment for examination of efficacy and safety of TAS-303 in female patients with SUI. This study consists of a single-blind observation period, a double-blind treatment period, and a follow-up observation period.

2.1.1. Primary Endpoint

Percent change in the mean incontinence episode frequency per 24 hours (Week 8 of treatment)

2.2. Target Sample Size

2.2.1. Target Sample Size

250 to be enrolled in the treatment period

2.2.2. Rationale for Sample Size Determination

The number of patients was determined, assuming that efficacy comparable to that of duloxetine can be expected based on results of nonclinical studies. Based on the mean rate of change in the number of urinary incontinence of -62.28% in the duloxetine group and -41.86% in the placebo group from data of a clinical trial of duloxetine, Yentreve clinical study results, Trial ID #6231, the difference between the TAS-303 6-mg or 3 mg group and the placebo group in the rate of change in the number of urinary incontinence, which is the primary endpoint of the present study, was assumed to be -20%. From the standard deviation of 33.73% in the duloxetine group and 32.08% in the placebo group in the above study data, the standard deviation common in two groups was assumed to be 35%. Using the two-sided significance level of the entire test of 5% and the two-sided significance level of each test of 2.5% by Bonferroni's method, when the statistical power is specified as 90% and the rate of withdrawal in the treatment period as about 5%, the number of patients necessary for confirmation of a significant difference between the TAS-303 group and the placebo group is approximately 250 (83 per group).

3. DATA AND ANALYSIS POPULATIONS USED FOR STATISTICAL ANALYSIS

3.1. Materials and Data Other Than Case Report Form

Materials and data necessary for statistical analysis other than the case report form are listed in Table 3-1.

Table 3-1 Materials or Data Necessary for Statistical Analysis Other than Case Report Form

Item	Materials or data	Remarks
Attribution of patients	Flag for attribution of each patient to each analysis population	To identify attribution of each patient to each analysis population.
	List of patients excluded from analysis populations with reasons	To list patients excluded from analysis populations
Information on randomization	Key code, allocation adjustment factor at the time of allocation	To identify the treatment group and for analyses with the allocation adjustment factor
Information on deviation	Details of deviation, significant deviation flag	To list patients with deviations
Coding to MedDRA terms	Correspondence table between AEs by investigators and AEs in MedDRA terms (English to Japanese)	To tabulate the incidence of AEs using standardized terms.
	Correspondence table with MedDRA terms for medical history and complications	To list medical history and complications in MedDRA terms
Institutional reference value	Institutional reference values for laboratory test values	To evaluate normal/abnormal laboratory values
Drug name	Correspondence table between concomitant medications by investigator and WHO Drug Dictionary	To tabulate grouped concomitant medications and specify the order

3.2. Analysis Populations

The name of analysis populations and their definitions are shown in Table 3-2. The handling of patients with problems in terms of their attribution apart from the criteria shown below will be determined through discussion by the sponsor, the medical experts, and other personnel. The primary efficacy analysis population is PPS while the primary safety analysis population is all treated population.

Table 3-2 Definition of Analysis Populations

Analysis Populations	Definition
All screened population	All patients who gave informed consent
All observation period enrolled population	All patients enrolled in the observation period of this study
All treatment period enrolled population	All patients enrolled in the treatment period of this study
All treated population	Patients in the all observation period enrolled population who have received at least 1 dose of the study drug.
Full Analysis Set(FAS)	Patients in the all treatment period enrolled population who have received at least 1 dose of the study drug for the treatment period and have at least 1 available efficacy endpoint before start of the treatment period and during the treatment period.
	Patients in FAS who have not met any of the following criteria: (1) Patients that have violated any inclusion criteria (2) Patients that have met any exclusion criteria (any criteria that affects the efficacy evaluation)
Per Protocol Set(PPS)	(3) Patients whose compliance rate is < 80% during the treatment period (4) Patients whose rate of completion of Bladder diary (status of urinary incontinence) is < 70% at Week 8 of treatment
	(5) Patients that have received any prohibited concomitant medications or prohibited concomitant therapies that may affect the efficacy evaluation

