### 4.3 Patient Discontinuation Criteria

When patients meet the following conditions, administration of the study drugs is discontinued. Discontinuation criteria for individual patients are shown below.

- (1) When continuation of treatment is difficult because of onset of an adverse event
- (2) When the patient requested the withdrawal of consent
- (3) When a serious noncompliance with the study implementation procedures was noted
- (4) When continuation of the study became impossible due to a move, transfer to another hospital, busy schedule or other reasons of the patient
- (5) When a patient was found not to fulfill the criteria for subjects of this study (not meeting the inclusion criteria or meeting the exclusion criteria)
- (6) When the following liver damage for which a causal relationship with the study drugs of this study cannot be denied occurred
  - 1) AST (glutamic oxaloacetic transaminase [GOT]) or ALT (glutamic pyruvic transaminase [GPT]) > 8 × ULN
  - 2) AST (GOT) or ALT (GPT) > 5 × ULN persisting for 2 weeks or longer
  - 3) AST (GOT) or ALT (GPT) > 3 × ULN with total bilirubin (T-Bil) > 2 × ULN or international normalized ratio (INR) > 1.5
  - 4) AST (GOT) or ALT (GPT) > 3 × ULN and onset of malaise, nausea, vomiting,

right upper quadrant pain/tenderness, pyrexia, rash or eosinophilia (> 5%)

- (7) When a patient became pregnant
- (8) When the effect of the study drugs was insufficient or symptoms were exacerbated and the Investigator or Sub-investigator considered that the study should be discontinued
- (9) Other cases in which the Investigator or Sub-investigator considered the discontinuation of the study necessary

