#### (1) Drugs and therapies for SUI

- Clenbuterol hydrochloride
- Chinese herbal medicine or other related products (Hochuekkito, processed food containing medicinal Cucurbita pepo seed extract and soy germ extract [PEP])
- Tricyclic antidepressants (imipramine hydrochloride, amitriptyline hydrochloride, clomipramine hydrochloride, etc.)
- Estrogen
- $\alpha$  adrenergic receptor agonists (ephedrine, phenylpropanolamine, midodrine, methoxamine, etc.)
- Duloxetine
- Surgical treatment (TOT procedure, TVT procedure, etc.)
- Physical therapy (pelvic floor muscle training, feedback training, biofeedback training, vaginal cone, electric stimulation therapy, magnetic stimulation therapy, etc.)

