#### **13.1.3.2 Primary Endpoint Analysis**

The following analyses are performed regarding the rate of change in mean number of urinary incontinence per 24 hours at Week 8 of the treatment period from baseline, which is the primary endpoint.

- (1) Main analysis
  - In PPS, the difference between the TAS-303 6 mg group and the placebo group and the difference between the TAS-303 3 mg group and the placebo group are

tested by t test using the two-sided significance level of the entire test of 5%. To consider multiplicity, the significance level for each comparison is adjusted by Hochberg's method.

(2) Sensitivity analysis of main analysis

- The evaluation in (1) is performed in FAS. Missing values are imputed using last observation carried forward (LOCF).

(3) Secondary analysis of primary endpoint

The following analyses are performed in FAS and PPS.

- Summary statistics are calculated for each treatment group. Missing values are not imputed.
- The rate of change from baseline in mean number of urinary incontinence per 24 hours for each week was analyzed using mixed-effect models for repeated measures (MMRM) to estimate the therapeutic effect of TAS-303 at Week 8 of the treatment period.
- In PPS and FAS, intergroup comparison is performed by the Wilcoxon rank sum test. Missing values are imputed by LOCF.

(4) Analysis by allocation factor

- The primary endpoint is analyzed for each condition of urinary incontinence (SUI and MUI).
- The primary endpoint is analyzed for each category of mean number of urinary incontinence per 24 hours (less than 2/day and 2 or more/day).

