6.1.3. Treatment Compliance Endpoints

6.1.3.1. Compliance Rate

The definition of compliance rate during observation and treatment periods is shown below.

• Observation/Treatment periods discontinued patient

If there is no dose Modification/Interruption/Discontinuation at all, the compliance rate is 100%, and if "Yes" is selected for dose Modification/Interruption/Discontinuation, the following formula shall apply.

[1] Observation period

Observation period compliance rate (%) = $100*[Total\ Treatment\ Days\ (Dose\ Modification/Interruption/Discontinuation\ were not\ included)] / [The larger of 21 and (the last dose date in Observation Period - the first dose date in Observation Period + 1)]$

[2] Treatment period

Treatment period compliance rate (%) = 100*[Total Treatment Days (Dose Modification/Interruption/Discontinuation were not included)] / [The larger of 56 and (the last dose date in Treatment Period - the first dose date in Treatment Period + 1)]

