7.2. Sensitivity Analysis of Primary Analysis

The primary analysis will be performed in FAS. Any missing values will be imputed using the last observation carried forward (LOCF) method. Analyses will be performed in the same fashion if no imputation takes place.

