7.3. Secondary Analyses of Primary Endpoint

Following analyses will be performed in FAS and PPS:

- Summary statistics will be calculated for each treatment group. Missing values will not be imputed.
- For percent change in the mean IEF per 24 hours from baseline at each week, mixed-effect models for repeated measures (MMRM) will be performed using treatment groups, evaluation time points (Week 4 and Week 8 of treatment), and interactions between the treatment group and the evaluation time point as fixed effects, and allocation factors (status of urinary incontinence [SUI or MUI], mean IEF per 24 hours [≥ 2 per day or < 2 per day]) and age (≥ 60 years or < 60 years) as covariates. Thus, the least mean square (LS Mean) in each treatment group and the difference in the LS mean between each dose group and the placebo group and the two-sided 95% CI will be estimated at Week 8 of treatment. Unstructured covariance structure will be assumed, and toeplitz type will be used in case of no convergence. If convergence is still not achieved, the First-order autoregressive → Compound symmetry → Variance component will be used in this order. The Kenward-Roger method (2009)⁴⁾ will be used to calculate degrees of freedom.
- Intergroup comparison will be conducted using the placebo group as the control by the van Elteren test⁵⁾ using Wilcoxon rank sum test and allocation adjustment factors and age (< 60 years and ≥ 60 years) as strata. If any stratum includes a group with 0 patient, the test will be conducted by excluding age from the strata. The van Elteren

test will be performed in two patterns, i.e., a pattern in which allocation adjustment factors at the time of enrollment are used as strata (analysis in the FAS only) and a pattern in which allocation adjustment factors recorded in CRF are used as strata. Missing data will be imputed using LOCF.

• The time profile of percent change from the baseline will be graphically presented by treatment group.

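### The primary superiority test is run in the per-protocol set, which drops patients for post-randomisation reasons; the same test in the FAS is only a sensitivity analysis

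*SAP*

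**What the plan says.** The protocol and SAP agree on the primary test. Protocol 13.1.3.2 (1) sets it out with the words "In PPS, the difference between the TAS-303 6 mg group and the placebo group", and likewise for 3 mg, as a t-test at two-sided 5% overall with Hochberg's adjustment. SAP 7.1 repeats this, and SAP 3.2 names the population: "The primary efficacy analysis population is PPS while the primary safety analysis population is all treated population".

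The PPS (Protocol Table 13.1.2.1-1, SAP Table 3-2) is the FAS minus patients who meet any of five criteria. Two concern eligibility. The other three are compliance below 80% in the treatment period, Week 8 diary entry below 70%, and prohibited drugs or therapies considered to influence efficacy evaluation. For a patient who discontinued, the compliance denominator in SAP 6.1.3.1 is "The larger of 56 and (the last dose date in Treatment Period - the first dose date in Treatment Period + 1").

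The FAS version of the test appears under the sensitivity heading of both documents. SAP 7.2 says "The primary analysis will be performed in FAS", with LOCF and also without imputation. Protocol 13.1.2.2 analyses wrongly dosed patients by drug received in the PPS and by allocated group in the FAS. SAP 7.3 adds an MMRM in both sets, with the contrast against placebo that "will be estimated at Week 8 of treatment".

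**The concern.** This is a superiority comparison with placebo, and its 5% error rate rests on comparing the groups as randomised. Patients may stop because of an adverse event or, under Protocol 4.3, "When the effect of the study drugs was insufficient or symptoms were exacerbated". If they stop early enough they fail the compliance criterion and leave the primary comparison, so the PPS is close to a completers set. If such exclusions differ by arm and are related to outcome, the PPS difference is biased and the familywise level is not assured.

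The direction cannot be predicted. Patients who stop for lack of effect may do worse than average. Patients removed for using items that Protocol 7.4.1 lists under "Drugs and therapies for SUI" may do better.

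The FAS test and the table of exclusions by arm (SAP 9.1) would expose a discrepancy. Neither document says what follows if the PPS and FAS disagree, so the PPS result would still decide the primary objective.

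**Working it through.** **The plan's own figure.** Inputs from SAP 2.2.2: difference 20, SD 35, two-sided 0.025 per comparison, power 90%, withdrawal about 5%. The normal formula gives n = 2 × 35² × (2.241 + 1.282)² / 20² = 76.02, so 77 per arm, and 77/0.95 rounds up to 82. The noncentral t gives 78, and 78/0.95 rounds up to 83, or 249 in total. The stated 83 per group (about 250) is reproduced. The 5% covers withdrawal only; no allowance for other PPS exclusions is stated.

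**Compliance cut-off.** 0.8 × 56 = 44.8 days. A patient who discontinues after 44 dosing days has 44/56 = 78.6% and is excluded. One with 45 days has 80.4% and stays.

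**Bias with no drug effect.** Assumptions: every arm has mean change −41.86 (the placebo figure in SAP 2.2.2), SD 35, and 250/3 patients. A fraction p is excluded, with mean e. The values of p and e are assumed, because the documents give none. Both active arms are treated alike.

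- Retained mean = (−41.86 − p·e)/(1 − p).
- Bias = active retained mean minus placebo retained mean; a negative value favours the drug.
- SE = 35 × √(1/n_active + 1/n_placebo), with n = (250/3)(1 − p).
- Per-comparison error is the two-sided 0.025 rejection rate of a normal variable shifted by bias/SE.
- Familywise error is by simulation with a shared placebo arm, rejecting if the larger p ≤ 0.05 or the smaller p ≤ 0.025.

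| Excluded, active v placebo | Mean of excluded | Retained means | Bias | SE | Per-comparison error | Hochberg familywise error |
|---|---|---|---|---|---|---|
| 5% v 5% | −20 | −43.01 v −43.01 | 0 | 5.56 | 2.5% | 4.8% |
| 7% v 5% | −20 | −43.51 v −43.01 | −0.49 | 5.59 | 2.6% | 4.9% |
| 10% v 5% | −20 | −44.29 v −43.01 | −1.28 | 5.64 | 2.9% | about 5.5% |
| 10% v 5% | −60 | −39.84 v −40.91 | +1.06 | 5.64 | 2.8% | about 5.2% |
| 15% v 5% | 0 | −49.25 v −44.06 | −5.18 | 5.72 | 9.2% | about 16% |

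In the fourth row the tail favouring the drug falls to 0.8%, from 1.25%. The last row is deliberately extreme. Swapping the arms reverses each sign. Equal exclusions of similar patients, or excluded patients at the overall mean, give no bias.

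**Power cost of making the FAS primary.** Noncentral t, SD 35, two-sided 0.025. For the PPS, n = (250/3)(1 − loss) and the difference is 20. For the FAS, n = 250/3 (all randomised patients assumed to be in the FAS), and the difference is 20 × (1 − loss) if excluded patients show no drug effect, or 20 × (1 − loss/2) if they keep half of it.

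| Would be excluded from PPS | PPS power | FAS, no effect in excluded | FAS, half effect in excluded |
|---|---|---|---|
| 10% | 89% | 85% | 89% |
| 15% | 87% | 81% | 87% |
| 20% | 85% | 75% | 85% |

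**The case against.** Five points can be made for leaving the plan alone.

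- **The harm shown is modest.** Moderate imbalance moves familywise error from 4.8% to about 5.5%, with a bias of about 1 point against an assumed effect of 20. This stands, and it limits the severity.
- **The drug-favouring scenario is not the natural one.** With no drug effect, stopping for lack of effect gives no reason for an excess on active; the excess would have to come from something else, such as tolerability. If the drug works, such exclusions would be expected more on placebo and would count against it. This also stands, and it is why the direction is left open.
- **The FAS with LOCF is not neutral.** Take the same null case with 10% v 5% affected. If patients who would have averaged −41.86 are assigned 0% change, the bias is (0.10 − 0.05) × 41.86 = +2.1 points and per-comparison error is 3.6%. If they are assigned −20%, the figures are +1.1 points and 2.8%. The FAS also requires an on-treatment efficacy value. This is a real limit on the choice of imputation. The 0% case is an upper bound, since it applies only to patients with no post-baseline diary value. It does not argue for discarding these patients.
- **Prohibited therapy is not purely post-randomisation.** The prohibition begins at enrolment in the observation period (Protocol 7.4.1). That is correct, but the compliance and Week 8 diary criteria arise only after randomisation.
- **This is phase IIa, with a consistent, pre-specified PPS and blinded decisions.** Blinding prevents exclusions chosen with knowledge of arm, but not exclusions caused by treatment. The plan also sets a 5% familywise level and sizes the trial for a significant difference, so the error rate is meant to count.

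**Conclusion.** The concern holds. Both documents let a set shaped by post-randomisation behaviour decide the primary objective, while the comparison that keeps the allocated groups is subordinate. That follows from the text and needs no assumption.

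The consequence is conditional. It requires exclusions that differ by arm and are related to outcome. In the moderate cases above the bias is about 0.5 to 1.3 points in either direction, and familywise error is about 4.9% to 5.5%. Much larger distortion needs an extreme pattern. All of these figures rest on assumed exclusion rates and assumed outcomes among those excluded. The point should be fixed because the remedy is already in the plan, but it does not by itself invalidate the trial.

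**What to change.** **If the key code has not been broken:**

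- In Protocol 13.1.3.2 and SAP 3.2 and 7.1, make the FAS, grouped as allocated, the primary population for the Hochberg-adjusted Week 8 comparison, and make the PPS supportive.
- Name one estimator: the FAS t-test with LOCF already in SAP 7.2, with the MMRM Week 8 contrast of SAP 7.3 reported beside it. The unimputed FAS t-test should not be primary, because it again drops patients without Week 8 data.
- FAS entry needs only one efficacy endpoint on treatment, not necessarily a diary value. State what LOCF does when there is no post-baseline diary value. Baseline carried forward (0% change) is one option, with the bias shown above. Report the number of such patients per arm.
- List randomised patients outside the FAS by arm and reason.
- Reconcile SAP 11.6, which says no efficacy subset is planned, with the use of the PPS.

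**If the key code has been broken:** do not re-designate. Report the FAS result with equal prominence, show PPS exclusions by arm and reason (SAP 9.1), and log the change as made after unblinding (SAP 10). The SAP history records version 2.0 as prior to key code breaking but does not state the timing of version 3.0.

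**Cost:** before unblinding, wording only, since both analyses are already planned. The effect estimate may be smaller. Power falls by up to about 10 points (85% to 75%) if 20% of patients would have been excluded and show no drug effect, and not at all if they keep half the effect.
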